The elusive and byzantine pathophysiology of autism engenders a marked challenge for health care providers; nevertheless, one technology that has demonstrated auspicious outcomes is low-level laser therapy (LLLT). Operating under the auspices of photochemistry, LLLT uses photonic energy to modulate the behavior and function of cells; this is accomplished by stimulating molecular entities capable of absorbing discrete wavelengths. For instance, cytochrome c oxidase (CCO), a terminal enzyme of the respiratory change, contains a tetrapyrrole prosthetic group that has been shown to absorb 635nm. Photon-induced activation of CCO increases cell bioenergetics, which, in turn, activates intra-cellular secondary signaling cascades that in turn affect growth factor synthesis, cell proliferation, cytokine production, and expression of specific transcription factors. Studies have reported increased adenosine triphosphate (ATP) synthesis along with activation of the intracellular redox state following the production of reactive oxygen species (ROS). As an essential bio-catalyst, ATP lowers the activation for pivotal biochemical reactions within cells. Concerning neurons, laser irradiation has been shown to promote the recovery of injured peripheral nerves and the spinal cord. Moreover, studies have revealed that excitable cells like neurons can be directly stimulated by light, enhancing the action potential of the cell increasing the release of neurotransmitters such as glutamate and acetylcholine.

Influence of the intracellular redox state enables LLLT to affect two well defined transcription factors, NF-kB and activator protein-1 (AP-1). The laser induced shift towards a more oxidized (alkalized) state impacts redox-sensitive transcription factors and subsequent gene expression. Recent evidence indicates that laser therapy can significantly diminish the expression of COX-2 by affecting the regulatory system controlling NF-kB, resulting in the reduction of inflammation. By suppressing the mechanism that upregulates inflammation, the application of laser irradiation can serve as a non-invasive means to down-regulate inflammatory agents reducing the severity of acne perhaps even preventing its onset.

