RESULTS: The complete results analysis for the ABC assessment tool, for each individual Subscale score and the Global score are presented below. Subscale I: Irritability/Agitation was the primary efficacy outcome measure of interest.

(i) ABC Subscale and Global Scores

Table 1 below shows the mean and standard deviation of the Baseline (pre-treatment) and Endpoint (after the final treatment administration) scores and the change that occurred across the two measures for each of the 5 ABC Subscale Scores and the Global Score.

Table 1: Mean, Standard Deviation and Change of Baseline and Endpoint ABC Subscale and Global Scores

	Baselin	ne (n=11)	Endpoint (n=11)		Change (n=11)	
	Mean	St. Dev.	Mean	St. Dev.	Mean	St. Dev.
Subscale I: Irritability/Agitation	14.45	8.18	5.36	6.70	-9.09	6.76
Subscale II: Lethargy/Social Withdrawal	11.36	7.16	4.00	4.31	-7.36	5.64

Subscale III: Stereotypic Behavior	7.36	5.20	3.64	3.23	-3.73	3.55
Subscale IV: Hyperactivity & Noncompliance	18.00	11.93	6.91	6.20	-11.09	9.40
Subscale V: Inappropriate Speech	6.18	3.37	2.73	1.35	-3.45	2.46
Global Score	57.36	31.56	22.64	19.22	-34.73	25.84

A series of t-tests for 2 correlated samples was conducted to evaluate the significance of the change in Baseline to Endpoint ABC Subscale and Global scores. The Baseline to Endpoint changes were found to be statistically significant for all 5 subscale scores and for the Global Score of the ABC, as shown in Table 2 below.

Table 2: T-test Results for Baseline to Endpoint Changes in ABC Subscale and Global Scores

	µа-µв	t	df	p(two- tailed)	р
Subscale I: Irritability/Agitation	9.09	+4.46	10	0.0012	p<0.005
Subscale II: Lethargy/Social Withdrawal	7.36	+4.33	10	0.0015	p<0.005
Subscale III: Stereotypic Behavior	3.73	+3.48	10	0.006	p<0.01
Subscale IV: Hyperactivity & Noncompliance	11.09	+3.91	10	0.003	p<0.005
Subscale V: Inappropriate Speech	3.45	+4.65	10	0.00091	p<0.001
Global Score	34.73	+4.46	10	0.0012	p<0.005

ADVERSE EVENTS: there were no adverse events reported or observed for any of the 11 subjects throughout the duration of the pilot study, and no subject showed any negative score changes from Baseline to Endpoint.

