Eighty per cent (80%) of all 40 active procedure group subjects met the Positive Responder Rate compared with no (0%) placebo group subjects. Chi Square analysis found the differences between each of the 3 active procedure groups and the placebo group to be statistically significant, at p<0.0001.

ABC Global and Subscale Scores Across Study Duration: Mean change in each of the ABC Global Score and 5 Subscale Sores across study duration between procedure groups was evaluated through ANOVA analysis. Mean changes in scores for test group subjects decreased progressively and sizably across study duration including during a 4-week follow-up period during which time no procedures were administered, with the changes found to be statistically significant for each of the 3 active procedure groups (p<0.0001). Conversely, all scores were essentially unchanged across study duration for placebo group subjects and not statistically significant, at p>0.05.

CGI-S Scores: Change in CGI-S scores across study duration between procedure groups was evaluated. At baseline, all subjects (100%) in both procedure groups were rated in the top 3 severity of condition ratings of '5: Marked', '6: Severe' or '7: Amongst the most extreme of all patients with this condition'. CGI-S scores improved progressively and substantially across study duration for each of the 3 active procedure group subjects but not for placebo group subjects. By Week 8, all placebo group subjects (100%) retained a 5-7 CGI-S rating while only 35% of all 40 active procedure subjects retained a 5-7 CGS-S rating.

CGI-C Scores: Change in CGI-C scores across study duration between procedure groups was evaluated. CGI-C ratings for each of the 3 active procedure group subjects demonstrated continuous progressive improvement in symptom presentation across study duration. By Week 8, the presentation of symptoms and behaviors of autistic disorder for 85% of all 40 active procedure group subjects were reported as being 'Very Much Improved' or 'Much Improved' Conversely, there was essentially no change in CGI-C ratings across study duration for placebo group subjects.

6 Month Long-Term Follow-Up Evaluation: All 19 subjects originally randomized to the placebo subject group completed an additional 6-month post-procedure evaluation. Each of the outcome measures continued to demonstrate meaningful progressive improvement.

Adverse Events: No adverse event was reported for or by any subject throughout study duration.

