- ➤ Each subject will receive a total of eight study treatments with the Erchonia® HLS laser device, two treatments per week for 4 consecutive weeks, each treatment administration 3 to 4 days apart.
- > Each study treatment will be administered by the study investigator at the study test site.
- > Each study treatment administration will last 5 continuous minutes.

The treatment administration process is as follows:

- 1. The patient is seated comfortably.
- 2. The patient is correctly fitted with the KenTek Corporation KGOG-6101 light blue Medium Goggles safety goggles.
- 3. The Erchonia® HLS laser is positioned perpendicular to and 4 inches above the skin surface of the right temporal region.
- 4. The laser is activated and applied systematically in a slow continuous free-hand sweeping motion laterally from the right temporal region across the back of the head to the left temporal region and back again across the same location on the back of the head to the right temporal region and so forth back and forth for 5 continuous minutes.

The temporal region of the head is in the lateral regions of both the right and left sides of the head over the temporal bone, behind the eye between the forehead and the ear and above the zygomatic arch. The back of the head in this protocol is defined as the area across the base of the parietal bone of the cranium extending laterally between the bilateral temporal regions. The locations and treatment processes are illustrated in the image below.

- 5. HLS Spectrum laser is turned off.
- 6. The safety goggles are removed from the subject.
- 7. The treatment session is complete.

STUDY EVALUATION TIMELINE

The study evaluation phase is as follows:

- ✓ Treatment Administration Phase: 4 weeks
- ✓ Post-treatment Evaluation Phase:
 - 4 weeks for all subjects

The evaluation time points and associated measures to be evaluated during the study are as follows:

TREATMENT ADMINISTRATION PHASE: 4 WEEKS

At Each of the 8 Study Treatment Administration Visits

- Medication and therapy use review
- > Adverse events evaluation

WEEK 2 END: Study Midpoint

Following completion of the first 2 weeks of the Treatment Administration Phase (after the 1st 4 treatments), the following study measures will be recorded:

- Aberrant Behavior Checklist (ABC)
- Clinical Global Impressions (CGI)

WEEK 4 END: Study Endpoint

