- (iii) The **Fischer's Exact categorical analysis technique** for comparison of proportion of successes (accurate procedure group assignment determination) and failures (inaccurate procedure group assignment determination) between subject

- groups will be performed for each of the caregiver and assessment investigator determinations.
- (iv) **Qualitative analysis confirmation:** Evaluation of the comments provided by the caregiver and assessment investigators in the rationale section to explain the guess at group assignment will be evaluated and interpreted as follows to either support or negate the numerical findings:
 - Positive blinding efficacy will be supported through qualitative assessment of comments provided to support perceived group assignment that pertain to the determination being made based on treatment efficacy or lack thereof; e.g.: 'My child has been calmer and communicating better lately, so I think he got the real treatment' or 'I haven't noticed any change in my child's behavior at all, so I believe he got the fake treatment.'
 - Blinding will be determined to have failed if comments provided to support perceived group assignment pertain to factors such as sensation/visual clues, such as 'I saw/didn't see a light go on the laser', or other factors that pertain to blinding having been compromised such as 'I overheard the doctor saying my child was/wasn't getting the real treatment.'

SAFETY ANALYSES

Safety analyses will be completed on all subjects who were randomized to treatment group and received at least the first study treatment administration with the Erchonia® HLS Laser device.

Safety will be assessed by evaluating and comparing frequency and incidence of observed and/or reported adverse events between test and placebo treatment groups. A chi-square test with a continuity correction will be performed to compare the percentage of subjects who had adverse events and/or reactions between the test and placebo group subjects.

SAFETY AND CONFIDENTIALITY ISSUES

ADVERSE EVENTS

At any time throughout the study, any adverse event reported by a subject and/or subject's caregiver and/or observed by the study investigator will be recorded on the case report form and subsequently evaluated by the Principal Investigator for its relation to the study treatment and whether or not any corrective action need be taken. All applicable adverse events will be reported to the IRB and EC, if applicable.

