Formal evaluation of the occurrence of any adverse events will take place at the end of each study treatment administration and each evaluation visit. In addition, subjects/caregivers will be instructed to contact the investigator at any other time that he or she believes a potential adverse event has occurred throughout the subject's participation in the clinical study.

The investigator will record the observation or report of any adverse event and assign the relationship to the study treatment on the appropriate case report form in the subject's file and will report the occurrence to the governing IRB, if and as appropriate, within 5 days of the reported occurrence, or within 24 hours in the occurrence of a serious adverse event including death.

The only known potential adverse event associated with the use of laser devices is that long-term exposure to laser light could cause damage to eyesight. As a precaution, during all laser treatment administrations with the Erchonia® HLS at the test site, both the subject and the administration investigator will wear safety glasses that filter out the laser light spectrum. The administration investigator will wear KenTek Corporation KenTek C22-KMT-6101 light blue safety glasses and the subject will wear KenTek Corporation KGOG-6101 light blue Medium Goggles safety goggles. Additional information on this safety eyewear is contained above on pages 6-8 under the section titled: DEVICE SAFETY: RISK AND PREVENTION OF EYE INJURY.

There are no other known potential adverse events from application of the study lasers. There have been no observed or reported adverse events or reactions to the application of the family of Erchonia® laser devices in several other studies using these laser devices. However, potential adverse events that may occur include, but are not necessarily limited to: skin irritation, skin discoloring, skin rash, skin indentations and infection. There may also be unknown or unanticipated risks to using the laser devices with this study treatment.

MONITORING OF THE CLINICAL STUDY

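### Adverse event evaluations are scheduled but their content is not stated; no events in 59 earlier courses suggests that, with recording unchanged, the safety comparison would be close to 0 v 0

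*Combined protocol and SAP*

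**What the plan says.** Under Safety and Confidentiality Issues, Adverse Events, "any adverse event reported by a subject and/or subject's caregiver and/or observed by the study investigator will be recorded on the case report form". The same section adds a schedule: "Formal evaluation of the occurrence of any adverse events will take place at the end of each study treatment administration and each evaluation visit". Between visits, "subjects/caregivers will be instructed to contact the investigator at any other time" if they suspect an event. The Study Evaluation Timeline lists an adverse events evaluation under "At Each of the 8 Study Treatment Administration Visits" and again at Week 8, but not in the Week 2 or Week 4 lists.

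The Adverse Events section gives damage to eyesight as the only known risk and names as possible events "skin irritation, skin discoloring, skin rash, skin indentations and infection". The Safety Analyses section of the statistical analysis plan compares the percentage of subjects with adverse events between arms by a chi-square test with continuity correction, in all randomised subjects who received at least one treatment.

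Under Supportive Clinical Data, the earlier randomised trial is summarised as "No adverse event was reported for or by any subject throughout study duration". For the feasibility study, "there were no adverse events reported or observed for any of the 11 subjects throughout the duration of the pilot study".

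**The concern.** The schedule says when events are evaluated, not how. No section available defines an adverse event, says whether intercurrent illness or injury counts, or gives a question or symptom list. The protocol names eye and skin events without directing anyone to ask about them.

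The earlier results make this more than a drafting gap. They show no event of any kind, including in children given sham treatment, so a benign device cannot be the whole explanation. Under-recording could explain it, and so could a definition that leaves out background illness.

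The between-arm comparison is the only safety analysis planned, and the Study Rationale presents the device as possibly free of side effects, which this trial is meant to help show. If recording works as it seems to have done before, a result of no events would describe the recording and not the device. The exclusion criteria admit children with a documented mental age from 18 months, so the caregiver has to be the main source.

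**Working it through.** **Inputs from the documents.** Earlier trial: 21 active, 19 placebo and 19 cross-over courses, evaluated to Week 8, with no adverse events (Supportive Clinical Data, study 2). Current trial: 20 per arm (Subject Sample Size) and a continuity-corrected chi-square (Safety Analyses). **Assumed:** background all-cause risks of 5%, 10% and 20% per course, because the documents give none.

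**1. The plan's own figure.** n per arm = 2 × [8.9 × (1.960 + 0.842)/8.5]² = 17.2, rounded up to 18. Then 18/0.89 = 20.2, stated as 20. This reproduces to within rounding. It is set by the efficacy endpoint; no power or precision is given for safety.

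**2. How surprising is zero?** Courses: 21 + 19 + 19 = 59, in 40 children. P(no events) = (1 − p)^n:

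| Assumed risk p | n = 59 | n = 40 (randomised only) |
|---|---|---|
| 5% | 4.8% | 12.9% |
| 10% | 0.2% | 1.5% |
| 20% | about 2 in a million | 0.013% |

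On the 19 sham courses alone, zero is unremarkable at 10% (13.5%) and unlikely at 20% (1.4%).

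**3. Forecast if recording is unchanged.** The one-sided 95% upper limit on the recorded rate is 1 − 0.05^(1/59) = 4.9% per course. Over 40 subjects that is 40 × 0.0495 = 2.0, or about one per arm at most. The predictive probability of 0 v 0 is (59 + 1)/(59 + 1 + 40) = 0.60 with a uniform prior and 0.77 with a Jeffreys prior. Using only the 40 randomised courses it is 41/81 = 0.51, or 0.71 with Jeffreys. On 59 courses, the probability of at most two subjects with an event in total is 0.94 to 0.98.

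**4. What the planned test can do at 20 v 20.** For k v 0, the statistic is 40 × (20k − 20)²/[20 × 20 × k × (40 − k)].
- 5 v 0: 256,000/70,000 = 3.66, p = 0.056.
- 6 v 0: 400,000/81,600 = 4.90, p = 0.027.
- 0 v 0: the denominator is zero, so there is no result.

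The exact two-sided 95% upper limit for 0/20 is 1 − 0.025^(1/20) = 16.8%.

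**5. Effect of incomplete capture.** Assumed true risks of 60% v 10%, exact enumeration:

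| Captured | Recorded risks | Power | P(0 v 0) |
|---|---|---|---|
| All | 60% v 10% | 89% | negligible |
| Half | 30% v 5% | 38% | 0.03% |
| A quarter | 15% v 2.5% | 5% | 2.3% |

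Here the harm is lost power, not a 0 v 0 table. With recorded rates of 20% v 0%, P(0 v 0) = 0.8^20 = 1.2%.

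**6. Does prompting dilute the test?** Take an assumed device-caused risk of 30%. With background risk b, the active-arm risk is 1 − 0.7(1 − b). Power at full capture is 58% for b = 0 (30% v 0%), 25% for b = 20% (44% v 20%) and 11% for b = 40% (58% v 40%). At half capture, the recorded risks of 15% v 0%, 22% v 10% and 29% v 20% give 7%, 7% and 5%.

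**The case against.** A reader might infer three stronger things, and the documents do not support them.
- *That capture is passive only.* It is not. Formal evaluations are scheduled, caregivers are told to call between visits, and Monitoring of the Clinical Study requires documented staff training in identifying and reporting adverse events. What the text available lacks is the content of the evaluation.
- *That the earlier trial used the same method.* Its method is not described. Its one-line result speaks of events reported, not observed; the reported-or-observed wording belongs to the feasibility study and the current plan. Counting only device-related events, or brief summarising, would also produce zero.
- *That the comparison will be near 0 v 0 whatever the device does.* Steps 5 and 6 rule this out: events noticed in a fifth of active children would almost never leave both arms empty.

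The strongest remaining objection is that the question wording belongs on the case report forms, which are in Appendix C and cannot be inspected here. That stands, and makes the point conditional. It is also fair that the background risks are assumptions, and that the 59 courses come from 40 completers, with 19 children counted twice. The 40-course column meets the double counting and still gives 1.5% at 10%. The ADI-R, required to confirm diagnosis, is described for mental ages above 2 years, which narrows the 18-month argument without removing the reliance on caregivers.

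A further objection is that prompting adds background events and weakens the single test. Step 6 confirms this, but the fall from 58% to 11% starts from full capture. At half capture there is almost no power to lose. The answer is to report by type with intervals, not to leave the evaluation unspecified.

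**Conclusion.** The point holds as a conditional one that the sponsor should act on. In the text available, evaluations are scheduled with no stated content, no statement that all causes count, and no instruction to ask about the named eye and skin events. Zero in 59 earlier courses has probability 0.2% at an assumed 10% all-cause risk (1.5% on 40 courses). It therefore suggests under-recording or a narrow event definition, and the documents cannot say which. At an assumed 5% the evidence is weaker (4.8% and 12.9%).

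If recording is unchanged, 0 v 0 has probability 0.60 to 0.77 (0.51 to 0.71 on the smaller denominator). The planned test would then be undefined, and a true rate of up to 17% per arm would remain compatible with the data. This rests on three things: that recording carries over, that the assumed background risks are reasonable, and that Appendix C does not already supply the missing content.

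**What to change.** In the Adverse Events and Safety Analyses sections:
1. State that events of any cause count, including intercurrent illness and injury.
2. Keep spontaneous reports and add one fixed yes/no checklist, put to the caregiver in identical words in both arms at the eight treatment visits and the Week 2, Week 4 and Week 8 evaluations. This also reconciles the Week 2 and Week 4 lists, which omit adverse events, with the rule that every evaluation visit includes them.
3. Cover eye or vision complaints, the named skin events and infection, neurological symptoms, and any other illness or injury. The protocol lists no neurological event as expected; that group is suggested by its own mechanism, "enhancing the action potential of the cell increasing the release of neurotransmitters such as glutamate and acetylcholine".
4. Report prompted and spontaneous events separately and by type, with per-arm rates and exact 95% intervals beside the planned test.
5. If Appendix C already holds such a list, name it as the source for the comparison.

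Cost: one case report form page and its Spanish translation, and a few minutes at visits already scheduled. The drawback is more minor background events in both arms, which dilute a single pooled test and make another report of zero events unlikely.

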The CGI is rated on a 7-point scale. The clinician is asked to rate the patient relative to his or her prior experience with other patients with the same diagnosis, with or without collateral information. The CGI is a robust measure of efficacy in many clinical trials and is easy and quick to administer.

CLINICAL GLOBAL IMPRESSIONS SCALE - SEVERITY OF ILLNESS (CGI-S)

The CGI-S is an observer (clinician)-rated scale that measures illness severity.

The physician rates the patient on the CGI-S according to the following question: "Considering your total clinical experience with this patient population, how ill is the patient at this time?"

0 = Not assessed 4 = Moderately ill 1 = Normal, not at all ill 5 = Markedly ill 2 = Borderline ill 6 = Severely ill

3 = Mildly ill 7 = Among the most extremely ill patients

CLINICAL GLOBAL IMPRESSIONS SCALE - GLOBAL IMPROVEMENT (CGI-I)

The CGI-I is an observer (clinician)-rated scale that measures global improvement or change.

The physician rates the patient's condition at each applicable evaluation visit according to how much the patient's condition has changed since baseline evaluation on the following CGI-I scale. The total improvement is rated whether or not, in the physician's judgment, it is due entirely to the study intervention.

0 = Not assessed 4 = No change

1 = Very much improved 5 = Minimally worse

2 = Much improved 6 = Much worse

3 = Minimally improved 7 = Very Much Worse

References

- ✓ Leon AC, Shear MK, Klerman GL, Portera L, Rosenbaum JF, Goldenberg I. A comparison of
- ✓ symptom determinants of patient and clinician global ratings in patients with panic disorder and depression. J Clin Psychopharmacol 1993; 13(5):327–31.

The **Spanish Editions** of the CGI-S and CGI-I that will be administered in this study are the published translations for 'Spanish for Mexico' translation as per the National Institute of Mental Health (NIMH), United States Department of Health and Human Services (HHS) and distributed by:

Mapi Research Trust [name] USA www.mapi-trust.org

CAREGIVER SATISFACTION WITH STUDY OUTCOME

The subject's caregiver is asked to rate how satisfied he or she is with any change in their child's autism symptoms and behaviors overall following completion of the laser administration procedures with the Erchonia® HLS by using the 5-point Likert scale presented below to respond to the following question:

"Overall, how satisfied or dissatisfied are you with any change in your child's autism symptoms and behaviors overall following the study procedures with the study laser device?"

- Very Satisfied
- Somewhat Satisfied
- Neither Satisfied nor Dissatisfied
- Not Very Satisfied
- Not at All Satisfied

The **Spanish Translation** of the study Caregiver Satisfaction with Study Outcome assessment tool that will be administered in this study will be performed by Language Scientific, Inc. The translated document will be supported by a notarized Certification of Translation

BLINDING EFFICACY EVALUATION TOOLS

Caregiver Perceived Group Allocation and Rationale

The caregiver records whether he or she believes that their child received the study treatment with the true or fake Erchonia® HLS and records verbatim his or her reasoning or rationale for this perceived determination.

Assessment Investigator Perceived Subject Group Allocation and Rationale

The Assessment Investigator records whether he or she believes the subject to have received the study treatment with the true or fake Erchonia® HLS™ and records verbatim his or her reasoning or rationale for this perceived determination.

The **Spanish Translation** of the study Blinding Efficacy Evaluation assessment tools that will be administered in this study will be performed by Language Scientific, Inc. The translated documents will be supported by a notarized Certification of Translation.

STUDY PROCEDURE PROTOCOL

PRE-TREATMENT ACTIVITIES

STUDY QUALIFICATION

SIGNING OF INFORMED CONSENT FORM

The PI will commence by presenting and reviewing in detail the items in the informed consent form with the individual's designated caregiver(s) and answer any questions he or she may have. To proceed, the individual's designated caregiver must willingly sign the informed consent form.

ASSIGNMENT OF SUBJECT IDENTIFICATION NUMBER

The subject will be assigned a unique subject identification number based upon his or her order of entry into the study.

Additional information about the informed consent and subject ID number assignment is contained in a later section of the protocol titled, "SAFETY AND CONFIDENTIALITY ISSUES."

SUBJECT GROUP RANDOMIZATION

Subjects will be randomly assigned to either Treatment Group A or to Treatment Group B, following the methodology outlined above in the STUDY DESIGN section of the protocol.

STUDY QUALIFICATION EVALUATION: INCLUSION/EXCLUSION CRITERIA

The following tools from the Study Test Battery to be used during Study Qualification Evaluation

- ➤ Diagnostic and Statistical Manual of Mental Disorders, 5th Edition (DSM-V)
- Autism Diagnostic Interview (ADI-R)
- Aberrant Behavior Checklist (ABC) Irritability Subscale
- Clinical Global Impressions Severity (CGI-S) scale

INCLUSION CRITERIA

- ➤ Male or female child or adolescent aged 5 to 12 years
- ➤ Subject has met Diagnostic and Statistical Manual of Mental Disorders, 5th Edition (DSM-V) for autistic disorder within the past 2 years, as diagnosed by a trained, qualified medical professional such as a pediatric neurologist, child psychiatrist or developmental pediatrician
- Diagnosis is confirmed by Autism Diagnostic Interview (ADI-R)
- > Subject demonstrates 'irritable' behaviors such as tantrums, aggression, self-injurious behavior, or a combination of such behaviors
- ➤ Subject's Aberrant Behavior Checklist (ABC) Irritability Subscale score is >=18
- Subject's Clinical Global Impressions Severity (CGI-S) scale score is >=4 (4=moderately ill)
- Subject's current therapeutic/intervention plan for treating his or her autistic disorder (educational/behavioral or other therapy; medication use; dietary interventions) has

- been consistent/stable over at least the past 3 months and the subject's caregiver agrees, and it is possible for, the subject to maintain his or her current therapeutic/intervention plan throughout participation in the clinical study.
- Subject's caregiver agrees, and it is possible for, the subject to abstain from partaking in new treatments to treat the subject's autistic disorder symptoms during participation in the study. This includes educational/behavioral therapy, dietary interventions, medications such as FDA-approved Risperdal® and Abilify® and other medications often prescribed for the treatment of other autism-related symptoms, such as anxiety, depression, or obsessive-compulsive disorder, including antipsychotic medications used to treat severe behavioral problem, and medications used to treat people with attention deficit disorder

EXCLUSION CRITERIA

- Subject has primary or concurrent diagnosis of another disorder or other identifiable genetic condition associated with the autism spectrum scale or with mental retardation, including:
 - ✓ PDD-NOS
 - ✓ Asperger's Disorder
 - ✓ Rett's Disorder
 - √ Fragile-X Syndrome
 - ✓ Childhood Disintegrative Disorder
 - ✓ Down Syndrome
- Seizure disorders (active), cerebrovascular disease or brain trauma as etiology of autistic behavior
- Current diagnosis of, and treatment for, bipolar disorder, psychosis, schizophrenia, or major depression
- Known neurological disease, such as encephalitis
- Significant sensory or motor impairment such as cerebral palsy
- > Diagnosis of epilepsy that is currently treated with anti-convulsant medication
- Previous significant head trauma
- Hearing loss requiring use of assistive devices such as hearing aids or cochlear implant
- > Significant visual impairment that cannot be adequately corrected with lenses
- > Documented mental age younger than 18 months
- > HIV and other autoimmune disorders
- > Active cancer or treatment for cancer within last 6 months
- Unstable cardiac disease, such as a recent cardiac arrhythmia (including atrial fibrillation, ventricular fibrillation and irregular atrial-ventricular conduction time), or recent congestive heart failure, or recent myocardial infarction
- Previous surgical interventions to the head/neck area
- Sensitivity to, or contraindication for, light therapy
- Participation in a research study within the past 30 days

BASELINE ASSESSMENT

DEMOGRAPHICS AND TREATMENT HISTORY

(i) Demographic Variables

The following demographic variables will be recorded for each subject:

- 1. Gender: male or female.
- 2. Age
- 3. *Ethnicity*: Caucasian, Hispanic, African American, American Indian, Asian/Pacific Islander, Other.

(ii) Medication and Treatment History

A list of the following information about a subject's current and past medication and therapy use will be recorded:

- ✓ All prescription and OTC medications used to date to treat the subject's symptoms of autistic disorder. Include information on daily dosage and duration of use, as applicable:
 - Current medications
 - Non-current medications
- ✓ All therapies (conventional and alternative) used to date to treat the subject's symptoms of autistic disorder. Include information on frequency and duration of application, as applicable:
 - Current therapies
 - Non-current therapies
- ✓ All current medications (prescription and OTC) and therapies (conventional and alternative) currently used for non-autism disorder related indications. Include information on medication dosages and duration of use and frequency and duration of therapy applications, as applicable, as well as the indications for which each is being used.

BASELINE EVALUATION

The following tools from the Study Test Battery to be used during Study Baseline Assessment:

- Aberrant Behavior Checklist (ABC)
- Clinical Global Impressions (CGI) Severity of Illness Scale (CGI-S) only

PROCEDURE ADMINISTRATION PHASE

GENERAL ASSESSMENT CONDITIONS

- Subjects will be required to maintain their regular medication and dosage schedule used to treat symptoms related to autism disorder throughout the study. Subjects will not be required to stop taking any medications used to treat their autism disorder symptoms or for any other indication, as already prescribed by a treating physician, throughout the duration of participation in the study.
- Subjects must agree to not start taking any new medications, or partake in any other new non-study treatments, or to change the dosages they take of current medications, to treat the symptoms of autism disorder, during study participation.
- Subjects must agree to notify the study investigator immediately if their treating physician makes any change to medication, medication dosage or other treatment plan. The PI will evaluate the information to determine, in his or her professional opinion, if the changes are substantial enough to warrant withdrawal of the subject from further study participation.

[figure not shown]
STUDY TREATMENT ADMINISTRATION PROTOCOL

- > The study treatment administration phase will extend over four consecutive weeks.
- ➤ Each subject will receive a total of eight study treatments with the Erchonia® HLS laser device, two treatments per week for 4 consecutive weeks, each treatment administration 3 to 4 days apart.
- > Each study treatment will be administered by the study investigator at the study test site.
- > Each study treatment administration will last 5 continuous minutes.

The treatment administration process is as follows:

- 1. The patient is seated comfortably.
- 2. The patient is correctly fitted with the KenTek Corporation KGOG-6101 light blue Medium Goggles safety goggles.
- 3. The Erchonia® HLS laser is positioned perpendicular to and 4 inches above the skin surface of the right temporal region.
- 4. The laser is activated and applied systematically in a slow continuous free-hand sweeping motion laterally from the right temporal region across the back of the head to the left temporal region and back again across the same location on the back of the head to the right temporal region and so forth back and forth for 5 continuous minutes.

The temporal region of the head is in the lateral regions of both the right and left sides of the head over the temporal bone, behind the eye between the forehead and the ear and above the zygomatic arch. The back of the head in this protocol is defined as the area across the base of the parietal bone of the cranium extending laterally between the bilateral temporal regions. The locations and treatment processes are illustrated in the image below.

- 5. HLS Spectrum laser is turned off.
- 6. The safety goggles are removed from the subject.
- 7. The treatment session is complete.

STUDY EVALUATION TIMELINE

The study evaluation phase is as follows:

- ✓ Treatment Administration Phase: 4 weeks
- ✓ Post-treatment Evaluation Phase:
 - 4 weeks for all subjects

The evaluation time points and associated measures to be evaluated during the study are as follows:

TREATMENT ADMINISTRATION PHASE: 4 WEEKS

At Each of the 8 Study Treatment Administration Visits

- Medication and therapy use review
- > Adverse events evaluation

WEEK 2 END: Study Midpoint

Following completion of the first 2 weeks of the Treatment Administration Phase (after the 1st 4 treatments), the following study measures will be recorded:

- Aberrant Behavior Checklist (ABC)
- Clinical Global Impressions (CGI)

WEEK 4 END: Study Endpoint

Following completion of the 4-week Treatment Administration Phase (after completion of all 8 treatment administrations), the following study measures will be recorded:

- Aberrant Behavior Checklist (ABC)
- Clinical Global Impressions (CGI)
- Caregiver Satisfaction with Study Outcome
- Caregiver Perceived Group Allocation and Rationale
- > Administration Investigator Perceived Group Allocation and Rationale

POST-TREATMENT EVALUATION PHASE

WEEK 8: All Subjects

Four weeks following completion of the 4-week Treatment Administration Phase (8 weeks after study onset), the following study measures will be recorded:

- ➤ Aberrant Behavior Checklist (ABC)
- Clinical Global Impressions (CGI)
- Medication and therapy use review
- > Adverse events evaluation
- > Caregiver Satisfaction with Study Outcome
- Caregiver Perceived Group Allocation and Rationale
- Administration Investigator Perceived Group Allocation and Rationale

STATISTICAL ANALYSIS PLAN

The aim of this study is to determine if the treatment effect of the Erchonia® HLS laser device for the active treatment group is greater than that for the placebo treatment group.

The study will be considered a success if, using the Intent-To-Treat (ITT) Last Observation Carried Forward (LOCF) analysis, the primary endpoint is statistically significant at the 0.05 level.

PRIMARY EFFICACY OUTCOME MEASURE

The primary efficacy outcome measure in this study is the mean change from baseline to study endpoint (end of the four-week treatment period) in the Aberrant Behavior Checklist (ABC) Irritability Subscale score.

Study success will be established through the detection of a minimum mean difference of -8.5 points between test and placebo groups in the change in ABC Irritability Subscale score from baseline to study endpoint (end of treatment week 4) adjusted for the baseline ABC Irritability Subscale score. The -8.5-point mean difference between treatment groups is considered clinically relevant with a SD of 8.9, a two-sided test with 80% power and a 5% level of significance.

Null Hypothesis: There is no difference in the mean change in ABC Irritability Subscale score from baseline to study endpoint adjusted for the baseline ABC Irritability Subscale score between active treatment and placebo groups, to the effect of less than -8.5 points.

